9.8 TOXICITY MANAGEMENT

Subjects who develop a new infection while undergoing treatment with bermekimab should be monitored closely. Administration of study injections should be interrupted if a subject develops an infection requiring IV anti-infective treatment or if an infection meets the definition of "serious" (refer to Section 9.2 DEFINITION OF SERIOUS ADVERSE EVENT (SAE) for definition). Study medication may be restarted once the physician determines that the infection has been successfully treated. Otherwise prohibited concomitant medications may be given if medically necessitated. Specifically, if a patient develops an intercurrent infection, then topical and/or oral antibiotic usage is permitted. If a patient experiences an intercurrent illness associated with pain for which oral analgesia is required, then otherwise-prohibited oral analgesics are permitted. Topical and/or oral antibiotic usage are not permitted for worsening of HS (except as specified in Section 2.11.2 Antibiotic Rescue Therapy. Prior to use, every attempt should be made to contact the Sponsor's Medical Director for direction on re-introduction of bermekimab therapy after prohibited medication administration.

If the subject must undergo elective surgery, the study injections must be interrupted 2 weeks prior to the surgery. If the subject must undergo emergency surgery, the study injections must be interrupted at the time of the surgery. The injectable study medication can recommence at least 2 weeks after surgery once the physician has examined the surgical site and determined that it has healed and there is no sign of infection.

10. STATISTICAL PLAN

This section provides the basis for the statistical analysis plan (SAP) for the study. The SAP may be revised during the study to accommodate amendments to the clinical study protocol, and to make changes to adapt to unexpected issues in study execution and data that may affect planned analyses. Analysis variables are listed in Section 8.

10.1 DETERMINATION OF SAMPLE SIZE

The primary efficacy endpoint is percent of patients who have a positive HiSCR score (achiever) at week 12. The positive HiSCR score is defined as $a \ge 50\%$ reduction in inflammatory lesion AN count (sum of abscesses and inflammatory nodules), and no increase in abscesses or draining fistulas in HS compared with the lesions counted at baseline. The sample size is calculated for the bermekimab weekly injection group (Treatment Arm 1) versus placebo group (Treatment Arm 3) comparison (the primary comparison).

Assuming a positive HiSCR score is achieved in 60% of intent-to-treat (ITT) patients treated in the bermekimab weekly injection group (Treatment Arm 1) versus 30% in placebo treated patients (Treatment Arm 3), then, for a randomization ratio of 1:1:1, a sample size of 126 patients (42 in each treatment group) is required for approximately 80% power at a 0.05 significance level using a 2-sided Pearson chi-square test. In order to account for possible dropouts and to provide adequate safety data, approximately 150 patients will be randomized and treated.

10.2 RANDOMIZATION

A centralized block randomization schedule with a 1:1:1 allocation ratio will be utilized using an electronic randomization system. Patients will be randomly assigned to Arms 1, 2, or 3. The randomization schedule will be stratified by two factors: prior biologic use (yes/no) and Hurley Stage (II/III).

10.3 ANALYSIS SETS

- The safety analysis set (SAF) population will consist of all patients who receive at least one dose of study medication and will be analyzed as treated.
- The modified intent-to-treat (mITT) population will consist of all randomized and treated patients.

10.4 PATIENT DISPOSITION

A listing of all patients prematurely discontinued from the study, along with reasons for discontinuation will be provided. In addition, the total number of patients for each of the following categories will be summarized.

- The total number of screened patients: met the inclusion criteria regarding the target indication and signed the informed consent
- The total number of patients in each analysis set (SAF, and mITT populations)
- The total number of patients who complete the study and discontinued the study, and the reasons for discontinuation

10.5 STATISTICAL METHODS

Continuous data will be summarized for each treatment group using the number of observations available (N), means, standard deviation (SD), minimums, medians, and maximums. Categorical data will be summarized for each treatment group using counts and percentages. All statistical tests will be two-sided unless otherwise noted.

10.5.1 Demography and Baseline Characteristics

Demographic and baseline characteristics will be summarized descriptively by treatment group.

10.5.2 Safety Analysis

The primary objective of this study is to evaluate the safety and efficacy of bermekimab. Safety endpoints will be evaluated by monitoring adverse events from clinical and laboratory reporting. The safety analysis will be based on the SAF population. A summary of safety results will be presented for each treatment group.

10.5.2.1 Analysis of Adverse Events

Adverse events reported in this study will be coded using the Medical Dictionary for Regulatory Activities (MedDRA) coding dictionary (version 22.0 or newer). Coding will be to lowest level terms. The verbatim text, the PT, and the primary SOC will be listed in patient listings.

Pre-treatment AEs are defined as those that develop or worsen in severity from the time the patient provides informed consent, prior to the first dose of study drug. Treatment emergent AEs (TEAEs) are defined as AEs that develop or worsen in severity following the first dose of study drug through the last study visit.

TEAEs will be grouped by MedDRA System Organ Class (SOC) and Preferred Term (PT) within SOC and will be presented for each treatment group. The number and percentage of patients experiencing AEs and TEAEs will be summarized by seriousness (SAEs), severity (grades 1-5), and relationship.

10.5.2.2 Other Safety

Vital Signs

Vital sign parameters (blood pressure, pulse, oxygen saturation, respiratory rate and body temperature) will be summarized descriptively by treatment group using actual values and change from baseline values.

Laboratory Tests

Clinical laboratory values will be converted to standard international units. Clinical laboratory (as described in the treatment plan) data will be listed for each subject. Laboratory data will be summarized descriptively by treatment group using actual values and change from baseline values. A listing will be provided for patients with grade 2 or greater laboratory AEs.

Electrocardiogram

12-lead ECG status (ie, normal, abnormal, clinically significant) will be summarized descriptively by treatment group.

10.5.3 Efficacy Analysis

In general, efficacy analyses will include all randomized and treated patients (mITT population) and will be analyzed based on the randomized treatment groups, regardless of the treatment they actually received.

In addition to the analyses that will be performed following the formal database lock at the end of the study at Week 36, an additional database lock may be performed at Week 16, and interim analyses utilizing unblinded efficacy data available as the study progresses, may also be conducted to help plan potential future development activities. An internal interim analysis committee (IAC) will be established to review the interim data and formulate recommended decisions/actions. The IAC will consist of at least a clinician and a statistician (neither of whom are involved in study conduct or compound development), one of whom will chair the committee, and may also include other members as required by the nature of the IAs. Details will be provided in a separate IAC charter, which will define the organization and roles and responsibilities of the committee, possible recommendations or requests, and the communication process following IA reviews. Results from the Week 16 DBL and/or interim analyses will not be disseminated to investigators or subjects participating in the study. In addition, results of the interim analyses will not be disseminated to individuals associated with the conduct of the study.

10.5.3.1 Primary Efficacy Analysis

For the primary efficacy endpoint, the two bermekimab treatment groups will be compared with placebo. To account for these two comparisons, testing will be done in a sequential manner, each at the 0.05 alpha level. The bermekimab weekly injection group (Treatment Arm 1) will be compared to the placebo group (Treatment Arm 3) first. If this test is significant at the 0.05 level, then the bermekimab every other week injection group (Treatment Arm 2) will be compared to the placebo group (Treatment Arm 3). Otherwise, the P-value for Treatment Arm 2 vs Treatment Arm 3 will be considered nominal. This method to control the type-1 error will only be implemented for the primary efficacy analysis variable.

The number and percentage of patients who have a positive HiSCR score (achiever) at week 12 will be presented by treatment group. Patients who terminate from the study early prior to week 12 will count as non-responders (non-achievers) in the primary efficacy analysis (Non-Responder Imputation). If a patient received rescue medication, the patient will be counted as a non-responder from the start of rescue medication. Additional treatment failure rules and sensitivity analyses will be discussed in the statistical analysis plan.

A Cochran-Mantel-Haenszel (CMH) general association test stratified by prior anti-tumor necrosis factor or IL-17 inhibitor therapy use (yes/no) and Hurley Stage (II/III) will be used to compare each bermekimab dose separately with placebo. The primary efficacy analysis population will be the mITT population.

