## 2.4.1.2. Per Protocol Analysis Set

The primary endpoint will also be analyzed using the per-protocol population, which includes participants who are generally compliant with the protocol.

Specifically, the per protocol population includes participants in FAS except those

- who did not meet the inclusion criteria 7 in the protocol as listed below:
  - A total body count of abscesses and inflammatory nodules (A+N) of at least 3.
- who met the exclusion criteria 10 in the protocol as listed below:
  - Has a draining fistula count of >20 at the baseline visit.
- who did not receive all scheduled study agent administrations prior to Week 12.

However, for those who discontinued the study agent prior to Week 12 will be included in the perprotocol analysis and the data handling rule specified in Section 5.2.2 will apply. Participants who were excluded from the per protocol analyses will also be summarized.

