# 5.2. Analysis Specifications

## 5.2.1. Level of Significance

Unless otherwise specified, all statistical testing procedures will be performed at a 2-sided significance level of 0.05. Multiplicity adjustment was planned for the primary endpoint as specified in protocol Section 10.5.3 to maintain an overall Type I error of 0.05 or less for the primary endpoint analysis. Nominal p-values will be reported for other secondary analyses.

However, since this is a Phase 2 trial and stricter multiplicity adjustment for the primary endpoint at an overall alpha level of 0.05 is not required; a less stringent type I error controlled will be implemented instead. The study would be considered as positive if any of the comparisons for primary endpoint analysis (weekly injection group vs placebo, and every other week injection group vs placebo) is less than or equal to 0.05. Therefore, an overall Type I error rate will be maintained at 0.1 or less for the primary endpoint analysis. Nominal p-values will be reported for secondary analyses.

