# 5.2.2. Data Handling Rules

No imputation will be performed for missing baseline values.

For the main analysis of primary endpoint of HiSCR at Week 12, participants who discontinued treatment will be considered as a non-responder from that point onward. The remaining missing data will be imputed as non-responder. Supplementary analyses will be performed and include (1) using observed data regardless of whether the participant discontinued treatment or have missing data, and (2) data after treatment discontinuation will be considered as missing, missing response will be imputed by multiple imputation methods under the assumption of missing at random. Similar data handling rules (i.e., main analysis with non-responder imputation and

2 supplementary analyses) will also be applied for HiSCR response over time through Week 16. The following data handling rules will be applied for other endpoints:

Binary secondary endpoints:

• Analyses will be similar to the main analysis of the primary endpoint. A participant who discontinued treatment will be considered as a non-responder from that point onward. The remaining missing data will be imputed as non-responder.

Continuous secondary endpoints:

- If a participant discontinued treatment, zero will be assigned to improvement or percent improvement. Remaining missing data will not be imputed. A MMRM model will adjust for missing post baseline data and all available data from the 3 treatment groups through Week 16 or from Week 16 through Week 36 will be included. Under the assumption of missing at random (MAR), the missing data will be accounted for through correlation of repeated measures in the model.
- In addition, supplementary analyses will be performed for the analyses related to (a) change from baseline in AN count (Section 5.4.3.2.2) and (b) change from baseline in HSSD past 24 hours pain (Section 5.4.3.5.3.2) endpoints using
  - Observed data regardless of whether the subject discontinued treatment or have missing data.
    - Data after treatment discontinuation will be considered as missing, missing data will be addressed by MMRM model.

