## 5.3.2. Estimands

#### Primary Estimand:

The **Composite Estimand** will be targeted for the primary endpoint. The Composite Estimand for the primary endpoint is defined by the following 5 attributes:

- Treatment:
  - Bermekimab 400mg q2w
  - Bermekimab 400mg qw
  - Placebo

Note: treatment regimen include protocol specified antibiotic rescue therapy/lesion intervention as needed.

- Population: Adult participants with moderate to severe Hidradenitis Suppurativa for at least 1 year.
- Variable: HiSCR binary responder variable at Week 12, where a participant who discontinues treatment is considered as non-responder after discontinuation.

- Intercurrent event: The intercurrent event of treatment discontinuation is addressed by the composite strategy, as reflected in the variable definition.
- Population-level summary: Difference in the proportion of participants achieving HiSCR at Week 12 between the bermekimab and placebo treatment groups.

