#### Supplementary Estimands for primary endpoint:

Supplementary Estimand 1

Same components as the primary estimand, except for the strategy used for treatment discontinuation:

Hypothetical strategy: assess the treatment effect as if the participants would not have discontinued treatment

Note: Under this hypothetical strategy, the data of HiSCR status after treatment discontinuation will not be used and will be set to missing in analysis.

Supplementary Estimand 2

Same components as the primary estimand, except for the strategy used for treatment discontinuation:

Treatment policy strategy: assess the treatment effect regardless of treatment discontinuation.

Note: Under the treatment policy strategy, the data of HiSCR status after treatment discontinuation will also be used in analysis.

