## 5.3.3. Data Handling

Participants who discontinued treatment prior to Week 12 will be considered HiSCR non-responder at Week 12. In addition, participants with missing lesion count evaluations at Week 12 will be considered as HiSCR non-responders at Week 12.

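### Protocol and SAP score antibiotic rescue in opposite ways for the primary endpoint, and the SAP does not declare the change; two lesser schedule conflicts also need reconciling

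*Protocol*

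**What the plan says.** **Protocol.** Section 10.5.3.1, on the primary analysis: "If a patient received rescue medication, the patient will be counted as a non-responder from the start of rescue medication". It leaves further failure rules and the sensitivity analyses to the SAP. Under section 2.11.2, rescue with minocycline or doxycycline may start at Week 4 or Week 8 if the AN count has reached 150% of baseline or more. The patient then stays in the study on a stable regimen.

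**SAP.** The primary estimand in section 5.3.2 notes that the "treatment regimen include protocol specified antibiotic rescue therapy/lesion intervention as needed". It names one intercurrent event: "The intercurrent event of treatment discontinuation is addressed by the composite strategy, as reflected in the variable definition". Section 5.2.2 says that "participants who discontinued treatment will be considered as a non-responder from that point onward", with remaining missing data also imputed as non-response. Section 5.3.3 repeats this for the endpoint visit: "Participants who discontinued treatment prior to Week 12 will be considered HiSCR non-responder at Week 12". None of these sections has a rule for rescue.

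**Lesser passages.**
- (a) The rescue trigger needs an AN count at Week 4 or 8. Protocol 5.1 and calendar 5.2.1 list no lesion count at those visits, while SAP 5.4.3.2.1 says lesions are counted at every visit.
- (b) The protocol 5.1 procedure block for Weeks 1, 3 and 5 says all subjects get two injections. Protocol section 3, calendar footnote 6 and SAP 1.2 and 1.5.2 place the two injections at Weeks 0 and 1.

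**The concern.** The conflict concerns how the primary endpoint is scored. The same patient can be a non-responder under one document and a responder under the other, so two Week 12 results could be reported from the same data.

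The direction is not fixed. Moving from the SAP rule to the protocol rule turns some responders into non-responders. In a bermekimab arm this narrows the difference from placebo; in the placebo arm it widens it. Nothing in the documents shows which would dominate.

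Timing matters because SAP 1.5.2 unblinds named sponsor staff at the Week 16 database lock. A choice between the rules made after that point could be seen as informed by the results.

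In the two lesser points, sites are given passages that do not agree.

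**Working it through.** **1. Does another rule catch rescued patients?**
- *Discontinuation:* no. Rescued patients continue (2.11.2). Protocol 5.3 requires discontinuation for prohibited therapies, the list in 2.9 does not name the rescue antibiotics, and 9.8 exempts them.
- *Supplementary estimands:* no. Both are defined as "Same components as the primary estimand, except for the strategy used for treatment discontinuation".
- *Per-protocol set (SAP 2.4.1.2):* no. It excludes patients who miss the AN-count criterion, those with more than 20 draining fistulas, and those "who did not receive all scheduled study agent administrations prior to Week 12". Rescue is not a criterion.
- *SAP 4.6:* it only summarises and lists concomitant treatments that could improve HS.

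So no planned analysis applies the protocol rule.

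**2. The plan's own figure.** Inputs (protocol 10.1): 60% vs 30%, two-sided alpha 0.05, 80% power, Pearson chi-square. With pooled p = 0.45,

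n = [1.960·√(2·0.45·0.55) + 0.842·√(0.6·0.4 + 0.3·0.7)]² / 0.3² = 42 per arm (80.0% power), as stated. At 150/3 = 50 per arm, power is 86.6%. The choice of rescue rule leaves the planned N unchanged.

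**3. Effect per patient.** 1/50 = 2.0 percentage points.

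**4. Who is affected.** AN must go from at least 1.5 times baseline to at most 0.5 times baseline: a fall of (1.5 − 0.5)/1.5 = 66.7%. At the minimum baseline of 3, that is from 5 or more (4.5 rounded up) to 1 or 0 (1.5 rounded down). HiSCR also requires no increase in abscesses or draining fistulas.

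**5. How many would matter.** Unstratified Pearson test, 50 per arm, as an approximation to the stratified CMH test: z = (p1 − p0)/√(2·p̄(1 − p̄)/50).

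| Bermekimab | Placebo | z | p |
|---|---|---|---|
| 30/50 | 15/50 | 0.30/0.0995 = 3.02 | 0.0026 |
| 25/50 | 15/50 | 0.20/0.0980 = 2.04 | 0.041 |
| 24/50 | 15/50 | 0.18/0.0976 = 1.85 | 0.065 |
| 24/50 | 14/50 | 0.20/0.0971 = 2.06 | 0.039 |

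At the boundary, one patient in Arm 1 (25 to 24) or in placebo (15 to 14) changes the result. From the planned 30/50 it takes 30 − 24 = 6 net reclassifications in Arm 1.

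**6. Range under assumed rescue rates.** Assume 60% vs 30% holds under the protocol rule. The SAP rule then adds (share rescued × share of rescued meeting HiSCR) to each arm. Power is at 50 per arm. The rescue and response rates are assumptions.

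| Rescued, bermekimab vs placebo | Rescued who respond | SAP rates | Difference (points) | Power |
|---|---|---|---|---|
| 10% vs 10% | 50% | 65.0% vs 35.0% | 30.0 | 86.2% |
| 5% vs 10% | 10% | 60.5% vs 31.0% | 29.5 | 85.3% |
| 5% vs 10% | 50% | 62.5% vs 35.0% | 27.5 | 79.5% |
| 5% vs 20% | 50% | 62.5% vs 40.0% | 22.5 | 61.7% |
| 10% vs 5% | 50% | 65.0% vs 32.5% | 32.5 | 91.4% |

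If no rescued patient responds, the two rules agree.

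**7. Lesser points.**
- (a) After baseline, counts through Week 16 are scheduled at Weeks 1, 3, 5, 7, 9, 12 and 16. With windows of 7 × week ± 3 days, Weeks 4 and 8 are days 25–31 and 53–59. The nearest count windows are days 18–24, 32–38, 46–52 and 60–66, so none overlaps.
- (b) Injections before Week 12: 2 × 2 + 10 = 14. With two also at Weeks 3 and 5, the total is 16.

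**The case against.** **Few patients are involved.** This stands. A rescued patient must worsen to 150% of baseline, stay on treatment, and then improve enough for HiSCR. Worsening disease may also lead to discontinuation at the investigator's judgement. One patient can tip any binary endpoint at its boundary, and six at the planned effect looks unlikely for so narrow a group. Under SAP 5.2.1 and 5.3.4 either bermekimab arm can make the study positive, so a change in Arm 1 alone need not change the conclusion. This limits the size of the problem but does not remove the conflict.

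**The SAP is open about rescue and may be revised.** This stands in part. Section 5.3.2 prespecifies its handling, and protocol section 10 lets the SAP change for amendments or unexpected issues. The SAP cites neither for rescue. By contrast, section 5.2.1 openly departs from the protocol on multiplicity: "a less stringent type I error controlled will be implemented instead". The available SAP text has no such statement on rescue, and its table of contents shows no section on changes from the protocol.

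**Rescue means antibiotics.** Largely stands. The protocol uses the word only in 2.11.2. Lesion intervention has its own rule in 2.11.3: the treated lesion counts as permanently present, and needing more than two interventions ends study treatment. The opposite scoring is therefore shown for antibiotics only. A definition in 10.5.3.1 would be a useful clarification.

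**The schedule points are editorial.** A lesion count can be done at an unscheduled visit (5.1, 5.2.2). The calendar carries the loading-dose footnote only at Weeks 0 and 1, and section 2.6 speaks of two initial loading doses without naming weeks. They are minor, but the passages still disagree.

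**Conclusion.** The concern holds as an inconsistency between the documents and should be fixed. For antibiotic rescue, protocol 10.5.3.1 and SAP 5.2.2, 5.3.2 and 5.3.3 give opposite Week 12 scores to a rescued patient who stays on treatment and meets HiSCR. The change is undeclared, and no planned analysis recovers the protocol result.

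The size is 2.0 points per affected patient, assuming 50 per arm. The total is unknown because no rescue rate is given, and the number affected may be small. The tipping counts rest on an unstratified test with placebo at the planned 30%. Points (a) and (b) are genuine but lesser.

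**What to change.** Before the Week 16 database lock and its unblinding:

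1. State one handling of rescue in protocol 10.5.3.1 and SAP 5.2.2, 5.3.2 and 5.3.3. If it departs from the protocol, declare and justify it in the SAP.
2. Say whether rescue medication means the 2.11.2 antibiotics alone, or also lesion intervention (2.11.3) and analgesics (2.11.1).
3. Run the other handling as a sensitivity analysis, and report the number rescued before Week 12 in each arm.

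For the lesser points, the clinical team should decide which wording stands; no reading is preferred here:

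- (a) Reconcile protocol 2.11.2, 5.1 and 5.2.1 and SAP 5.4.3.2.1 on lesion counts at Weeks 4 and 8.
- (b) Reconcile the protocol 5.1 block for Weeks 1, 3 and 5 with section 3, calendar footnote 6 and SAP 1.2 and 1.5.2 on the visits with two injections.

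**Cost.** A few SAP sentences, one clarification letter or amendment, and one extra run of the primary CMH analysis. Rescue antibiotic use is already captured on the eCRF (2.11.2), so the main point needs no new data. The cost of (a) and (b) depends on the wording kept.
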